5. SELECTION OF PARTICIPANTS AND CLINICAL SITES/LABORATORIES

5.1 Rationale for Study Population

Participants of any gender or race who are between the ages of 18-60 years old are eligible for entry into this study. We have chosen to limit our study to adult (ages 18-60) subjects due to evidence from previous studies that there may be different rates of response to given antigens between adult and pediatric populations (for instance, pediatric trials of dietary intervention have consistently shown that milk is the most common causative antigen in this age group, while studies in adult populations have suggested that other antigens including wheat are more likely to drive eosinophilia in adults.)^{23, 24}. Given this apparent difference in response, we will limit the study population to ensure that we can accurately identify responses to the different dietary regimens.

5.2 Inclusion Criteria

Individuals who meet all of the following criteria are eligible for enrollment as study participants:

1. Subject must be able to understand and provide informed consent
2. Have diagnosis of EoE (based on consensus criteria)¹
3. Are aged 18 to 60 years
4. Have histologically confirmed active disease ≥ 15 eosinophils/hpf in the esophagus within 12 weeks of screening visit
5. Symptomatic (have experienced symptoms within the last month prior to enrollment)
6. PPI confirmation. (As a part of the diagnosis of active EoE, it must be demonstrated that acid reflux disease is not the primary cause of the participant's symptoms by documentation that the participant has been on a high dose of PPI (at least one dose, once daily) for at least 8 weeks prior to a diagnostic endoscopy of EoE without histologic resolution (i.e., ≥ 15 eosinophils/hpf). (Due to the variety of doses and various PPIs available, the dose will be confirmed adequate at the discretion of the PI.)
7. Have a negative urine pregnancy test at screening if of childbearing potential. Females of childbearing potential must have a negative urine pregnancy test (β -hCG) prior to enrollment into the study (i.e., at screening). These participants must agree to use adequate birth control measures (e.g., condom, oral/injectable/subcutaneous contraceptives, intrauterine device, or sexual abstinence) during the study and for at least one month after the last dose of study drug which will be documented in the source documents.

5.3 Exclusion Criteria

Individuals who meet any of these criteria are not eligible for enrollment as study participants:

1. Inability or unwillingness of a participant to give written informed consent or comply with study protocol
2. Have been treated with topical swallowed steroids within the last 2 months or systemic steroids within the last 3 months
3. Have pathological eosinophilia in segments of the GI tract other than the esophagus determined by local review
4. Have been diagnosed with a GI malabsorption disorder (i.e., Inflammatory bowel disease, Crohn's disease) or Celiac disease
5. Are currently on dietary therapy avoiding milk or on a 6FED.
6. Have concurrent *H. pylori* gastritis or parasitic infection

7. Have history of anaphylaxis to milk (with current avoidance of milk)
8. Unable to complete study procedures, including EGD.
9. Have previously failed strict dietary therapy clearly documented with one of these regimens or topical steroid treatment (i.e. have not achieved histological remission of <15 eos/hpf after having been on 2 mg of budesonide per day or 1760 mcg of fluticasone per day for 8 weeks prior to the EGD).
10. Use of investigational drugs within one month prior to enrollment
11. Are concurrently receiving any of the prohibited medications listed in section 8.3
12. Not fluent in English
13. On immunotherapy for pollen (if not on maintenance therapy) or IgE-mediated food allergy.
14. Past or current medical problems or findings from physical examination or laboratory testing that are not listed above, which, in the opinion of the investigator, may pose additional risks from participation in the study, may interfere with the participant's ability to comply with study requirements or that may impact the quality or interpretation of the data obtained from the study.

6. KNOWN AND POTENTIAL RISKS AND BENEFITS TO PARTICIPANTS

6.1 Risks of Investigational Product or Intervention as cited in Investigator Brochure or Package Insert

Treatment with topical swallowed steroids

In the short term (such as the Phase 2 six week period steroid study interval), the primary risk is the development of oral thrush, which is a known side effect of topical swallowed steroid use⁶. Other reported concerns include behavior changes and difficulty sleeping. Such side effects are reversible with medication reduction or discontinuation. Risks from longer term use of topical swallowed corticosteroid are less well understood, but might include bone demineralization, trouble with elevated blood sugar or hypertension, and/or eye changes such as glaucoma or cataracts. However, these have not been commonly seen with use of inhaled steroids for other diseases such as asthma and have not yet been seen in any of the controlled studies with topical steroids for EoE. There is also a concern about the potential for adrenal suppression with chronic steroid use, and we will monitor for this with morning cortisol levels at the beginning and end of Phase 2. There is also a theoretical risk for immunosuppression due to the chronic use of high-dose swallowed inhaled steroids, although this has never been shown to occur in previous studies or in the collective experience of the centers involved in the trial.

6.2 Risks of Investigational Product or Intervention cited in Medical Literature

N/A

6.3 Risks of Other Protocol Specified Medications

N/A

6.4 Risk of Study Procedures

6.4.1 Treatment with Dietary Therapy

Minimal risk exists related to implementation of short-term dietary therapies in EoE. Dietary instruction regarding

tenets of each dietary therapy and nutrition-related recommendations will be provided by a Registered Dietitian,

NIH Approved 11/22/2017

who will show participants how to implement and make appropriate substitutions for foods eliminated to ensure nutritional adequacy. A central dietitian will develop standardized instructional materials for use at all of the participating sites.

6.4.2 Histology Scoring System (HSS)

The histology scoring system is a method to evaluate esophageal biopsies containing eosinophils for various features (ex: basal layer hyperplasia, dilated intercellular spaces, surface epithelial alteration, apoptotic epithelial cells), eosinophilic inflammation (peak count, eosinophil abscess, eosinophil surface layering), and lamina propria (fibrosis). There is no risk associated with the utilization of the HSS.

6.4.3 Study Survey

Each participant between the ages of 18 to 60 years old will be asked to complete several surveys, including PRO measures regarding both Health Related Quality of Life as well as disease-specific symptom scores and QOL measures in order to address their EoE symptoms and problems/ feelings related to eating. The data gathered from these questionnaires will be correlated with several biomarkers of interest that have been associated with EoE. These surveys will be conducted at baseline and the end of each study phase. There are no foreseeable physical discomforts or significant risks related to answering the PROs or study questionnaires. However, some questions may be difficult or uncomfortable for participants to answer. Participants may refuse to answer any questions that they are uncomfortable with. The participants may also feel inconvenienced by completing the questionnaires. The participant questionnaires typically take approximately 15 to 20 minutes to complete. All participants will be given ample time to complete the questionnaires. Please reference the table below for guidelines regarding study questionnaire completion.

6.4.4 Esophageal Biopsies

The risks associated with collecting additional esophageal biopsies (up to a total of four obtained from the proximal and/or distal esophagus) for research at the time of the endoscopy include: bleeding at the site of tissue (biopsy) collection, and a small chance of perforation (hole) of the stomach, duodenum, or esophagus. Perforation is the most severe gastrointestinal complication, but generally it is self-resolving and poses no life-threatening risk. Transient bacteremia as a result of diagnostic UGI endoscopy has been reported at rates as high as 8%, but the frequency of infectious endocarditis and other clinical sequelae is extremely low, such that current American Heart Association and American Society for Gastrointestinal Endoscopy guidelines do not recommend antibiotic prophylaxis with diagnostic UGI endoscopy solely to prevent infectious endocarditis.⁵⁴⁻⁵⁷ The risk of aspiration during endoscopy is miniscule. To minimize the risks of collecting additional biopsies during endoscopy, the procedure will be performed or supervised by a skilled endoscopist, and additional biopsies will only be collected if the endoscopist feels it is appropriate to do so. Some samples that are collected during an endoscopy for research purposes may be frozen and shipped to other hospitals, institutions, and testing companies for analysis. Data may also be shared. The data and/or samples will be de-identified per HIPPA and have no PHI associated with them. The data and/or samples will be used in a collaborative relationship between institutions, or testing companies receiving the data and/or samples. All of these samples will be shared under a MTA, or other applicable agreement.

6.4.5 Blood Draws

Risks associated with the collection of blood are bleeding, bruising, and swelling, dizziness, fainting and infection at the site where the blood is drawn. In general, these procedures will be performed by individuals with expert skills in phlebotomy. To minimize the additional risks associated with phlebotomy, blood will be obtained during

the standard placement of intravenous lines when possible. The amount of blood drawn will adhere to institutional policy.

6.4.6 Skin Testing For Allergies—Prick Testing

Skin testing for allergies may cause mild discomfort when the skin is pricked. Participants may experience symptoms such as itching, stuffy nose, red watery eyes, or a skin rash if they are allergic to the substance being tested. A rare but serious whole-body allergic reaction, known as anaphylaxis, may occur. Anaphylaxis can be life threatening, but this usually only occurs with intradermal testing, and the health care provider performing the skin testing will be prepared to treat this serious reaction.

6.4.7 Skin Testing For Allergies—Patch Testing

Skin patch testing for allergies may cause mild discomfort at the local site including rash, itching and skin redness.

6.4.8 Swallowed Glucocorticoids

Swallowed glucocorticoids may cause oral or esophageal candidiasis; if this is noted, it will be treated with topical or systemic anti-fungal therapy, as clinically indicated. Swallowed glucocorticoids may cause adrenal suppression which will be monitored by serum AM cortisol determination before and after the study protocol. If a depressed value of AM cortisol is found at study completion, this information will be provided to the primary doctor and patient.

6.5 Standard of Care Procedures Associated with This Study Esophagogastroduodenoscopy (EGD)

Endoscopy with biopsy is a well-established procedure. Few patients have unexpected or serious complications. Since it is considered standard of care for adult patients with EoE to have an EGD with biopsies within a six week time frame to monitor the disease when trialing new therapies (foods or medications), the EGDs with biopsies that are associated with this study are not study procedures. Endoscopies will be performed regardless of study participation as patients' standard of care, and additional endoscopic procedures will not be performed because of participation in this study. It is considered standard of care for biopsies to be collected from the esophagus, stomach, and duodenum during endoscopy, and biopsies from all of these sites will be collected during endoscopic procedures at all participating sites whenever possible. Biopsies collected from the stomach and duodenum are evaluated to determine study eligibility. Subjects may be included, without stomach or duodenal biopsies, if there is no clinical history of involvement of stomach or duodenum.

6.6 Potential Benefits

Standard therapies for EoE consist of allergy test-directed and empiric elimination dietary therapies, complete elimination of all dietary antigens requiring the exclusive use of elemental formula, or the chronic use of topical swallowed steroids. These therapies are all associated with risks and benefits. Comparing a minimally restrictive dietary elimination regimen to a more restrictive dietary regimen to control esophageal inflammation may permit earlier identification of a diet that controls symptoms and achieves remission. In addition, by limiting the number of potential reintroductions, this less restrictive diet has the potential to limit the need for endoscopies and attendant sedation and thus reduce risk to patients and costs to the health care system.

There are no guaranteed benefits for any study participant. Potential benefits to the individual participant would include the use of a less restrictive diet compared to the standard 6FED, as well as a reduction in the time to identification of a minimally restrictive effective diet

7. INVESTIGATIONAL AGENT /DEVICE/INTERVENTION

7.1 Investigational Agents/Devices/Interventions

Investigational Agent #1

Flovent HFA Inhalation aerosol: swallowed fluticasone propionate 1760mcg daily (in Phase 2), manufactured by GlaxoSmithKline.

7.1.1 Formulation, Packaging, and Labeling

Page 10 of Flovent Investigator's Brochure:

FP HFA (GSK Lab Code GR106642X) inhalation aerosol is a pressurized MDI for oral inhalation. Each inhaler consists of a white to off-white suspension of FP (micronized) in a liquefied HFA propellant (GR106642X) which is contained in an aluminium can sealed with a metering valve. The canister is presented in a plastic actuator fitted with a dust cap.

Ingredients include FP (micronized), and GR106642X (1,1,1,2-Tetrafluoroethane). No other excipients are included in the formulation. Stability is at most 18 months when stored under labeled storage conditions of 25°C. As further real-time stability data become available, the shelf life will be extended.

A placebo inhaler containing GR106642X propellant 75mg per actuation alone is also available.

7.1.2 Dosage, Preparation, and Administration

Page 14 of Flovent Investigator's Brochure:

For all products, storage should be at a controlled room temperature between 25-30°C in a dry place and not above 30°C.

7.1.3 Drug Accountability

Under Title 21 of the Code of Federal Regulations (21CFR §312.62) the investigator will maintain adequate records of the disposition of the investigational agent, including the date and quantity of the drug received, to whom the drug was dispensed (participant-by-participant accounting), and a detailed accounting of any drug accidentally or deliberately destroyed.

Records for receipt, storage, use, and disposition will be maintained by the study site. A drug-dispensing log will be kept current for each participant. This log will contain the identification of each participant and the date and quantity of drug dispensed.

All records regarding the disposition of the investigational product will be available for inspection.

7.1.4 Assessment of Participant Compliance with Investigational Agent

Compliance with the dietary therapies will be assessed via completion of a food diary that will be reviewed by a registered dietitian at regular intervals throughout the study.

Compliance with Flovent will be determined by the counter that is on the Flovent inhaler. Greater than 80% compliance will be deemed “good” compliance for the study; subjects with less than 80% compliance will be encouraged by study staff to adhere to study dosages. All non-compliance issues will be documented, and compliance that is <70% or >120% will be reported to the study sponsor.

7.1.5 Toxicity Prevention and Management

In order to measure potential systemic toxicity of FP we have chosen to measure AM serum cortisol levels as a measure of adrenal suppression. Cortisol will be collected at the Treatment Phase 2 and the EOT Phase 2 visits. If the AM cortisol is low at the EOT Phase 2 visit, then study staff will communicate this information to the subject’s primary care physician for appropriate follow-up care.

7.1.6 Premature Discontinuation of Investigational Agent

Study therapy may be prematurely discontinued for any participant for any of the following reasons:

1. The PI feels that the study treatment is no longer in the best interest of the participant.
2. The participant experiences an AE that the PI feels warrants discontinuation of the study therapy.

8. OTHER MEDICATIONS

8.1 Concomitant Medications

8.1.1 Protocol-mandated

N/A

8.1.2 Other permitted concomitant medications

Throughout the study duration, all participants are expected to maintain medications such as a PPI, oral or nasal allergy medications such as antihistamines and any asthma-related medications that were prescribed prior to study entry.

8.2 Prophylactic Medications

N/A

8.3 Prohibited Medications

N/A

Medication	Washout Time Prior to Screening Visit (i.e., Study Entry)
Anti-immunoglobulin E [IgE] mAb	6 months
Methotrexate, cyclosporine, interferon- α	3 months
Anti-tumor necrosis factor [TNF] mAb)	6 months
Other systemic immunosuppressive or immunomodulation agents	3 months
Oral or intravenous systemic steroids	3 months
Topical swallowed steroids	2 months
Other investigative biologic	1 month
Anti-IL 5 agents	3 months
Anti-IL 13 agents	6 months
Other investigative drugs or device	1 month

8.4 Rescue Medications

If a subject has a worsening of EoE symptoms, any treatment that the subject would take for EoE, besides the study drug, would then exclude the subject from the study. As such, there are no treatments that will be provided on study for “rescue therapy”.

9. STUDY PROCEDURES

9.1 Screening/Baseline Visit (Weeks -12 to -1)

The screening visit should occur at a maximum of twelve weeks and a minimum of 1 week prior to the enrollment visit. A research staff member will perform the informed consent process. After obtaining informed consent, the following study procedures will be performed and documented:

- Assess eligibility (inclusion and exclusion criteria)
- Collect Medical, surgical and diet history
- Vitals (height, weight, blood pressure, heart rate, respiratory rate, temperature)
- Demographics (age, gender, race)
- Physical exam performed by a study clinician or qualified staff member
- Collect stool sample (if possible) from subjects who have consented to stool collection

- Obtain up to 4 biopsies from the distal and proximal esophagus for research purposes (taken during standard of care EGD)
 - One of these esophageal biopsies will be used for EDP
- Research lab samples
 - Blood (6-10 mL) or saliva (1-2 mL for future genetic testing may be collected at this visit)
 - Blood for metabolomics (3-5 mL)
 - CBC with differential (2-3 mL)- if a CBC with differential was obtained clinically as part of standard of care within the screening period, obtain the results from the standard of care CBC
- Assessment of concomitant medications and therapies
- Pregnancy Test (urine)

Participants may qualify for rescreening if they are ineligible due to any of the reversible illnesses listed in the exclusion criteria if their condition improves while recruitment is ongoing and they still fall within the screening window.

Esophageal biopsies for research may be taken during a participant's standard of care EGD (SOC EGD). If the participant has had an EGD and biopsies performed prior to the screening visit, the results of the EGD may be used to determine eligibility if it falls within the four-week window prior to enrollment. EGDs performed at an outside institution may be used as baseline if the corresponding pathology report and slides are available and the eosinophil counts meet the inclusion criterion of ≥ 15 eosinophils/hpf. In cases where the local pathologist has concerns regarding the eosinophil count, slides may be sent to the CRPC for rapid review in order to verify eligibility.

The amount of blood drawn (clinical plus research) will follow the NIH clinical center guidelines "Guidelines for Limits of Blood Drawn for Research Purposes in the Clinical Center" (May 26 2012).

Stool samples may be collected from participants who have consented to stool collection at the Screening/Baseline visit. If it is difficult to obtain the stool sample at this visit, it may alternatively be collected at the Enrollment visit. Stool will only be collected at some, but not all, participating centers.

9.2 Enrollment (Week 0)

All eligible participants will be enrolled into the study at Week 0 if they meet all entry criteria and have completed the screening procedures. Study procedures will not be repeated if the enrollment visit takes place within 5-10 business days of the screening visit. At this visit, staff members will:

- Assess eligibility (inclusion and exclusion criteria)
- Measure vitals (blood pressure, heart rate, respiratory rate, temperature), height and weight
- Obtain stool sample (if possible and not collected at Screening/Baseline) from subjects who have consented to stool collection
- Administer patient reported outcome questionnaires, which will include dietary questionnaires to measure *intake* of the food allergens and a food diary to assess baseline diet
- Completion of DSQ
- Assess concomitant medications and/or therapies

- Skin testing for allergies including prick and patch testing
- Randomize eligible participants to the 1FED or 6FED diet
- Provide standardized dietary instructions for 1FED or 6FED
- Research lab samples
 - Blood serum (~1-2 tsp, or 5-10 mL) for food IgE, CRD, and IgG4
 - Blood serum (~3-6 tsp, or 15-30 mL) for T cell studies

The participants will be encouraged to call the PI and/or study coordinator if they have any questions, concerns, adverse events, or changes in medication.

Stool samples may be collected from participants who have consented to stool collection at the Enrollment visit if they were unable to be obtained at the Screening/Baseline visit. Stool will only be collected at some, but not all, participating centers.

9.3 Phone Visits, Phase 1

A study staff member will conduct three phone visits (at weeks 1, 3, and 5) during Phase 1 in order to monitor participants' progress throughout the trial. The following procedures will occur during these phone visits:

- Assess con-med and/or con-therapy compliance
- Assess AEs
- Determine compliance with treatment
 - A dietary questionnaire to measure *intake* of the food allergens will be completed by the participants during weeks 1 and 5
 - A food diary will be completed by participants during weeks 1 and 5 to measure adherence
- Daily completion of the DSQ within the two weeks prior to the Phase 1 EOT EGD (Weeks 4 and 5)

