3.3 Secondary Objective(s)

- To extend Phase 1 of this study with a prospective non-blinded trial that determines the rate of remission following SGC in the 6FED non-responders and the rate of remission following 6FED in the 1FED non-responders (Phase 2).
- To extend Phase 1 of this study with a prospective non-blinded trial that determines the rate of remission following 6FED in the 1FED non-responders (Phase 2).
- To evaluate the effect of each therapy on histological remission defined by a variety of changes in eosinophils, including (a) pre- and post-therapy peak eosinophil counts; (b) partial remission (2-14 peak eosinophils/hpf); and (c) complete histological remission (≤ 1 peak eosinophils/hpf).
- To evaluate the effect of each therapy by utilizing the histology scoring system (HSS) created to express the severity and extent of other abnormalities in the gastrointestinal (GI) tract that often accompany eosinophilic inflammation.
- To evaluate endoscopic outcomes as assessed by the endoscopy scoring system (EREFS).
- To determine the impact of each therapeutic intervention on biomarkers using the EoE Diagnostic Panel (EDP).
- To evaluate the clinical and psychosocial effect of each therapy utilizing surveys to assess EoE symptoms and problems/feelings related to eating.
- To determine if any clinical parameters predict response to therapeutic intervention.
- To determine if any biomarkers including serum food specific IgE, CRD, and IgG4 predict response to therapeutic intervention.
- To determine if skin testing, in the form of prick and patch testing, predicts response to therapeutic intervention.
- To determine if milk-driven T cells in the blood positively correlate with milk atopy patch test results and effectiveness of dietary therapies.
- To bank DNA so that we can later elucidate genetic components of EoE

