- 2d. Assessment of milk-driven T cells.** In this sub-aim, we will perform exploratory studies designed to test the presence and significance of circulating milk-specific T cells in EoE patients. We will test the hypothesis that milk-specific T cells will be primarily CD4+, IL-5+, IL-13+, consistent with prior work.⁴⁷⁻⁴⁹ Furthermore, we will test the sub-hypothesis that the level of milk-specific T cells will positively correlate with positive atopy patch tests to milk and the response rate to milk elimination (1FED and secondarily 6FED, which also contains milk). The frequency of Th2 cells will be determined by FACS analysis, and milk-specificity will be estimated by milk protein stimulation in vitro, particularly looking at CD154 induction, a marker of T cell activation. These exploratory studies, will be performed with shipped blood samples, by [name], as published.^{47,48,50,51} The study will be limited to a pilot analysis of patients who only enter the 1FED and we will compare patients with positive and negative skin tests (prick and patch).
- 2e. Predictive Biomarker-analysis of EoE transcriptome.** In this sub-aim, we aim to identify biomarkers that may predict responsiveness to any or all of the treatment interventions associated with this trial. Determining such a biomarker would have a profound effect on disease management as patients could be quickly triaged into different therapies, e.g. diet versus SGC; thus saving time, reducing the number of endoscopies and potentially improving quality of life issues. As such, in this sub-aim, we will perform the EDP analysis on baseline biopsies, focused on identifying transcript levels that differentiate patients that respond to each of the interventions. In preliminary studies, we have conducted this type of analysis on patients that recently participated in the randomized controlled trial of high dose fluticasone (1760 mcg per day) for the treatment of EoE. Forty-two participants were enrolled in this study (28 FP, 14 placebo). After 3 months, 65% of FP-treated and 0% of placebo-treated participants had complete remission ($P = 0.0001$); 12% of FP-treated and 8% of placebo-treated participants had partial remission. Of the FP-treated participants in complete remission, 73% continued in complete remission, and 20% were in partial remission after halving the daily FP dosage.⁵³

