9.4 End of 1st Treatment phase or Early Withdrawal (Week 6)

For participants who have completed the 6 week Phase 1 or have withdrawn early from the study, the following procedures will occur:

- Measure vitals (blood pressure, heart rate, respiratory rate, temperature), height and weight
- Physical exam performed by a study clinician or qualified staff member
- Collect stool sample (if possible) from subjects who have consented to stool collection
- Administer patient reported outcome questionnaires
- Assess AEs
- Obtain up to 4 biopsies from the esophagus for research purposes (taken during SOC EGD)
 - One of these esophageal biopsies will be used for EDP
- Research lab samples
 - Blood serum (~1-2 tsp, or 5-10 mL) for food IgE, CRD, and IgG4
 - Blood serum (~3-6 tsp, or 15-30 mL) for T cell studies
 - Blood (6-10 mL) or saliva (1-2 mL) for future genetic testing may be collected at this visit (if not collected previously)
 - Blood for metabolomics (1 tsp, or 3-5 mL)
 - CBC with differential - if a CBC with differential was obtained clinically as part of standard of

care, obtain the results from the standard of care CBC

- Assess participant compliance with diet therapy and concomitant medications
- Pregnancy Test (urine)

Stool samples may be collected from participants who have consented to stool collection. Stool will only be collected at some, but not all, participating centers.

If a participant withdraws from the study before completing 6 weeks of dietary therapy, the end of treatment/early withdrawal visit should be conducted within one week of the participant's stopping dietary therapy. Participants should stay on their dietary therapy until results of biopsies are communicated to them.

Those participants who have resolution of their inflammation on endoscopy at the end of Phase 1 will complete the study at this time. Subjects with continued active inflammation will move on to phase 2, 6FED non-responders will start treatment with swallowed SGC (880mcg BID fluticasone propionate) and unrestricted diet and 1FED non-responders will start treatment of 6FED.

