10.2 T Cell Studies

We will test the hypothesis that milk-specific T cells will be primarily CD4+, IL-5+, IL-13+, consistent with prior work.⁴⁷⁻⁴⁹ Furthermore, we will test the sub-hypothesis that the level of milk-specific T cells will positively correlate with positive atopy patch tests to milk and the response rate to milk elimination (1FED and secondarily 6FED, which also contains milk). The frequency of Th2 cells will be determined by FACS analysis, and milk-specificity will be estimated by milk protein stimulation in vitro, particularly looking at CD154 induction, a marker of T cell activation. These exploratory studies, will be performed with shipped blood samples, by [name], as published.^{47,48,50,51} The study will be limited to a pilot analysis of patients who only enter the 1FED and we will compare patients with positive and negative skin tests (prick and patch).

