Research Lab Samples	EDP, other ^c	Serum food IgE, CRD, & IgG4; T cells				EDP, serum food IgE, CRD, & IgG4, T cells, other ^c				other ^c
Morning cortisol (serum)							X			X
CBC with differential	X					X				X
Stool sample	X ^d	X ^d				X				
Pregnancy test (urine)	X					X				X
Assess AEs			X	X	X	X	X	X	X	X
Provide food diary	X		X		X			X	X	
Provide instructions for diet or medication		X					X			
Determine compliance with treatment			X		X			X (diet)	X (diet)	X (SGC)
Dispense SGC							X			
Collect SGC										X
Collect compliance logs										X

^a First SOC EGD used to determine eligibility may be conducted within 4 weeks prior to enrollment visit.

^b This EOT SOC EGD pertains only to Phase 1 Non-Responders.

^c Other refers to collection of blood or saliva for future genetic testing. These samples will only be collected once, but may be collected at any of the visits indicated.

^d Stool samples may be collected at some participating centers from subjects who consent to stool collection. Stool may be obtained either at Screening/Baseline OR Enrollment, as well as at EOT Phase 1.

^e The DSQ should be completed daily in the 2 weeks prior to each endoscopy.

Each visit window (for visits 2-10) is ± 3 days.

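### Protocol sections 9.2 and 9.4 name serum as the specimen for the T cell studies, which conflicts with the cell-based assays the protocol describes

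*Protocol*

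**What the plan says.** The specimen for the T cell work is named in two visit lists. Protocol 9.2 (Enrollment, Week 0) orders "Blood serum (~3-6 tsp, or 15-30 mL) for T cell studies", and 9.4 (end of Phase 1, Week 6) repeats the line word for word.

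The assay is described in 4.4, sub-aim 2d, and again in 10.2: "The frequency of Th2 cells will be determined by FACS analysis, and milk-specificity will be estimated by milk protein stimulation in vitro". The readout of milk specificity is CD154 induction, an activation marker on T cells. On the material to be used, both sections say only this: "These exploratory studies, will be performed with shipped blood samples".

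The Schedule of Assessment has the Week 0 entry "Serum food IgE, CRD, & IgG4; T cells", with a semicolon between the serum tests and the T cells.

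The objective in 3.3 is "To determine if milk-driven T cells in the blood positively correlate with milk atopy patch test results and effectiveness of dietary therapies". The SAP's exploratory variables include a T-cell count and cytokine levels, and its exploratory objective 2(d) uses milk-driven T cells as a predictor of response.

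**The concern.** Serum is what remains after blood has clotted and the clot, with the cells, has been removed. A T cell cannot be counted, stained or stimulated in it. The visit lists are the text that site staff follow on the day, and they are the only place where a specimen type is stated for this assay. No section asks for whole blood, an anticoagulant or separated mononuclear cells.

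The same lists use plain *blood* for other samples, for example "Blood for metabolomics (1 tsp, or 3-5 mL" in 9.4. A coordinator could reasonably take *serum* on the T cell line as deliberate, the more so because the line above it, for food IgE, CRD and IgG4, is also labelled serum and is correct.

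At stake is the T cell sample at any site that reads the line literally. The Week 0 sample matters most. Randomization and diet instruction take place at that same visit, so a baseline sample lost there cannot be taken again before milk is eliminated. Section 15.1.1 adds an awkward consequence: since any departure from the procedures counts as a deviation, a site that drew the usable specimen would, on paper, be deviating from 9.2 and 9.4.

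**Working it through.** No sample size, alpha or power figure is involved. The check compares the wording across sections and then looks at the one number attached to the line, the volume.

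**1. Wording side by side**

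| Place | What it implies about the specimen |
|---|---|
| Protocol 9.2, Week 0 | Serum |
| Protocol 9.4, Week 6 | Serum (identical line) |
| Protocol 4.4 (2d) and 10.2 | Blood, shipped; assays need living T cells |
| Schedule, Week 0 | T cells set apart from the serum tests by a semicolon |
| Schedule, Week 6 | T cells in a comma-separated list; no separation |
| Protocol 3.3, objective | T cells in blood |
| SAP, exploratory variables | T-cell count, which needs cells |

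The two visit lines agree with each other and conflict with the assay sections, the objective, the SAP count variable and the Week 0 Schedule entry. The Week 6 Schedule entry is neutral.

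**2. What can be measured in serum**

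- Th2 frequency by flow cytometry: no, because it counts cells.
- CD154 induction after milk stimulation: no, because it needs viable T cells.
- T-cell count in the SAP: no.
- Cytokine levels in the SAP: not decidable. The SAP gives neither method nor matrix, and the point does not rely on this variable.

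**3. The stated volume**

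At 4.93 mL per teaspoon:

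- 3 × 4.93 = 14.8 mL
- 6 × 4.93 = 29.6 mL

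This reproduces the protocol's 15–30 mL, so the two units are consistent with each other.

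Does 15–30 mL look like a volume of serum or of blood drawn? The documents give no serum yield. Assuming that serum is 40–60% of the blood drawn, the draw needed for 15–30 mL of actual serum would be:

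- at 60%: 15 / 0.60 = 25 mL to 30 / 0.60 = 50 mL
- at 40%: 15 / 0.40 = 37.5 mL to 30 / 0.40 = 75 mL

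The protocol states no such draw. It also attaches the word serum to ordinary draw volumes elsewhere: about 5 mL for morning cortisol (9.5, 9.7) and 5–10 mL for food IgE, CRD and IgG4 (9.2, 9.4). The 15–30 mL therefore reads most naturally as the volume of blood to be drawn, with the wrong specimen label. That is an inference, and it depends on the assumed yield.

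**The case against.** The strongest reply is that nobody intends to run flow cytometry on serum. The sections that define the assay say blood, the objective says blood, the Week 0 Schedule entry separates T cells from serum, and the volumes look like blood draws. This stands. It makes the point an inconsistency to reconcile, and not a flaw in the design of the T cell study. It does not remove the point, because the two lines that are wrong are the operative ones.

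A second reply is that an error of this kind would be noticed. Section 17.6 gives laboratories online forms to verify receipt and report specimen problems, so a laboratory that received serum for flow cytometry could raise it. The glossary also lists a Manual of Procedures, which may name the tube. The first part stands as a limit on the damage, although it would not bring back baseline samples already taken. The second cannot be weighed either way, because that manual is not among the documents.

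A reader might infer that the whole T cell data set would be lost, or turn the draw volumes into a total of wasted blood. The documents do not support that. It would require every site to follow the line literally and the error to go unreported throughout the trial, and no section fixes the number of patients in the pilot.

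A reader might also think that the blood must be shipped unseparated, or that the SAP would score an unusable sample as a zero count. Neither follows: 4.4 and 10.2 defer to published methods, and nothing in the SAP proposes filling T cell data with zeros.

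**Conclusion.** The conflict is real. As written, 9.2 and 9.4 specify a specimen on which the planned T cell assay cannot be run. It is probably a labelling slip, and its priority is low.

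The reach is narrow. Sections 4.4 and 10.2 describe exploratory studies limited to a pilot in patients who enter 1FED. The synopsis and 3.3 list the T cell correlation among the secondary items, but 13.4.5 and the SAP analyse it as exploratory. The primary endpoint, its alpha of 0.05, the power and the sample size do not depend on it.

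The amount of data at risk cannot be stated from the documents. It depends on how many sites read the line literally and how soon the laboratory reports it. What can be said is that any Week 0 sample processed to serum is lost for this aim for good. The conclusion rests on the meaning of serum as cell-free and on the absence, in the two documents, of any other specimen instruction for T cells.

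**What to change.** In 9.2 and 9.4, replace the serum label on the T cell line with a cell-containing specimen: anticoagulated whole blood or separated mononuclear cells, whichever the assay laboratory requires. Leave the serum label on the line for food IgE, CRD and IgG4, where it is right. Check that the Manual of Procedures says the same.

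The cost is two lines of protocol text and one check against the manual. No change to the SAP is needed.
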